## 5 INTRODUCTION

The purpose of the Population Pharmacokinetics (PopPK) analysis plan (AP) is to give details of the methodology and conventions that will be used for the PopPK analysis to be performed on the data from the GDX-44-015 study entitled:

*Gadopiclenol Pharmacokinetics, Safety and Efficacy in Pediatric Patients < 2 Years of Age Undergoing Contrast-enhanced MRI.*

The PopPK AP ensures the credibility of all study findings by means of predefined data analysis plan. The modelers prepared the PopPK AP with the objective to finalize it before starting the analysis.

## 6 ANALYSIS OBJECTIVE

The objective of the analysis will be:

- To assess whether the PopPK model previously developed for adults and children aged 2-17 years of age for gadopiclenol is predictive of exposure for the pediatric population aged up to 23 months (inclusive);
- To update the PopPK model previously developed for adults and children aged 2-17 years of age with data obtained in pediatric population <2 years from the GDX-44-015 study;
- To search population specific covariates that can explain any difference between pediatric patients < 2 years and older patients;
- To predict PK parameters and exposure in pediatric patients <2 years receiving IV injection of gadopiclenol for Contrast-enhanced MRI;
- To simulate PK parameters and exposure in pediatric patients <2 years receiving IV injection of other doses of gadopiclenol (0.025 mmol/kg, 0.1mmol/kg).

## 7 STUDY GDX-44-015

### 7.1 STUDY OBJECTIVES

#### 7.1.1 Primary Objective

To evaluate the pharmacokinetic profile of gadopiclenol in plasma following single intravenous injection of 0.05 mmol/kg body weight (BW) in pediatric population aged up to 23 months (inclusive) scheduled for a contrast-enhanced MRI examination of any body region including central nervous system (CNS).

#### 7.1.2 Secondary Objectives

1. To evaluate the safety of gadopiclenol (clinical and biological) up to 3 months following single administration.
2. To evaluate the efficacy of gadopiclenol-enhanced MRI by body region (CNS, vessels and pool of others) as assessed by on-site Investigator.

### 7.2 SUMMARY OF STUDY DESIGN

This Phase II open-label, uncontrolled, multicenter trial is designed to investigate the pharmacokinetic (PK) profile of gadopiclenol in plasma, in pediatric population <2 years, using a population PK approach. This

	PH21036 / GDX-44-015 Analysis Plan Version 2.0: 29/10/2024	gadopiclenol Page 8/30
---	---	---------------------------

approach, which allows sparse blood sampling, is selected to minimize the clinical burden to children. Blood sampling will be recommended via indwelling catheters rather than by repeated venipunctures.

Inclusion will be started using an age-down staggered approach. Three age groups are defined:

- Group 1: patients aged 3 to 23 months (inclusive)
- Group 2: patients aged 28 days to less than 3 months;
- Group 3: patients aged from birth to 27 days (term newborns).

The inclusions was initially planned to start with the oldest patients (Group 1) and end with the youngest patients (Group 3) (cf. protocol V2.0 dated 21 July 2022). However, following the protocol amendments (cf. protocol V4.0 dated 9-Oct-23) the aged-down staggered approach was discontinued to allow the inclusions in Group 3 (patients aged from birth to 27 days).

The previous age group will be completed in parallel with the start of the next group.

### 7.3 TREATMENTS

**Investigational Medicinal Product (IMP) Name:** gadopiclenol (formulation G03277.100)

**Pharmaceutical form:** 3 mL of sterile, clear, transparent ready-to-use aqueous solution for injection contained in vials of 10 mL.

**Concentration:** 0.5 M

**Route and method of administration:** The IMP will be administered intravenously (IV) manually or by power injector (if the desired volume can be delivered by the injector) as a bolus injection at a recommended rate of 1-2 mL/sec.

Contrast-enhanced MRI can start shortly after the injection depending on the pulse sequences used and the protocol for the examination. Gadopiclenol injection will be followed by a saline flush to ensure complete administration of the contrast.

Patients will be dosed according to their body weight (BW) on the day of MRI examination. Gadopiclenol will be administered at a dose of 0.05 mmol/kg BW (0.1 mL/kg BW).

The patient's participation starts from the signing of the Informed Consent Form by the parent at V1 (screening) and ends at V5 (3-month safety follow-up) or earlier in case of premature discontinuation.

The date of the last visit (date of the last procedure related to the visit) of the last patient undergoing the trial will correspond to the end of the trial.

### 7.4 STUDY POPULATION

50 patients will be included in the trial, according to the inclusion and exclusion criteria and assuming that at least 45 patients will be evaluable for the PK.

Patients will be distributed between the 3 age groups as following:

- Group 1: at least 20 patients
- Group 2: at least 12 patients
- Group 3: at least 5 patients

At least 25 patients (50%) will be scheduled to undergo contrast-enhanced MRI of CNS (CNS cohort)

	PH21036 / GDX-44-015 Analysis Plan Version 2.0: 29/10/2024	gadopiclenol Page 9/30
---	---	---------------------------

## 7.5 PK SAMPLING

The start of IMP administration is set as time point 0 (T0), and 3 blood samples will be collected per patient (one sample will be obtained during the 10-60 minutes time window, the second sample will be obtained during the 2.0-4.0 hours' time window and the third sample will be obtained during the 6.0-8.0 hours' time window post-injection). For each patient, within each time window, the sampling time points will be allocated by randomization, as per the [Table 1](#) below, at the inclusion visit, allowing a good estimation of PK parameters. Exact time of sample collection will be recorded.

**Table 1 Sampling time points randomly allocated.**

Time Window	Sampling time within Time Window (allocated by randomization)
W1: 10 min to 60 min post-injection	W1.1: 10 min to < 25 min post-injection W1.2: 25 min to < 35 min post-injection W1.3: 35 min to < 45 min post-injection W1.4: 45 min to 60 min post-injection
W2: 2.0 hours to 4.0 hours post-injection	W2.1: 2.0 hours to < 2.5 hours post-injection W2.2: 2.5 hours to < 3.0 hours post-injection W2.3: 3.0 hours to < 3.5 hours post-injection W2.4: 3.5 hours to 4.0 hours post-injection
W3: 6.0 hours to 8.0 hours post-injection	W3.1: 6.0 hours to < 6.5 hours post-injection W3.2: 6.5 hours to < 7.0 hours post-injection W3.3: 7.0 hours to < 7.5 hours post-injection W3.4: 7.5 hours to 8.0 hours post-injection

Further to the change in protocol V4 (dated 9 October 2024), the collection of PK samples from the same line used for the IMP injection, or alternatively the use of a capillary specimen (for example heel-pricks or finger pricks), in the event of any difficulties to place and/or maintain the peripheral intravenous line into a vein, were allowed.

## 8 STUDY DATA

### 8.1 JUSTIFICATION FOR THE NUMBER OF SUBJECTS

The sample size was determined in order to optimize the characterization of gadopiclenol pharmacokinetics, with a good precision of parameters, in pediatric population through popPK modelling, which is the study primary objective. Sample size determination was coupled with evaluation of the PK sampling scheme recommended by FDA for the evaluation of the PK of Dotarem® in the same population of pediatric patients aged between 0 and 2 years.

Simulations were performed in order to evaluate the performance of the design and the sample size, using gadopiclenol popPK model for adult and children aged between 2 and 17 years, refined to account for renal maturation in pediatric population <2 years.

The design evaluation was performed for a sample size of 45 subjects evaluable for the primary criteria, and for 40 subjects. Overall, the sampling design with either 45 or 40 subjects will allow to estimate all fixed parameters (clearances and volumes) with an excellent precision (Relative standard error (RSE) <=20%). The between subject variability for clearance (CL) and residual error will be also very well captured (RSE<30%). Only the variability for the central volume of distribution could be poorly estimated if the pediatric population <2 years data cannot be combined with other data (stand-alone pediatric population <2 years model).

With only 3 samples to be taken by pediatric population <2 years, it is anticipated that inter-individual variability (IIV) on volumes of distribution could not appropriately estimated, even with larger sample size. This is not considered as a relevant issue invalidating the sampling design, because this variability is of limited interest as far as the IIV for CL is correctly estimated. Increasing the sample size will moderately improve the estimation of the IIV on volume of distribution, in case of pediatric population <2 years data cannot be pooled with other data collected in adult, children and adolescents.

Assuming that about 10% of patients included in the trial will not be evaluable for the primary criteria, a sample size of 50 patients, in agreement with the pediatric plans (PIP/PSP), will allow to achieve the study objectives.

	PH21036 / GDX-44-015 Analysis Plan Version 2.0: 29/10/2024	gadopiclenol Page 11/30
---	---	----------------------------

## 8.2 DEFINITION OF POPULATION

### 8.2.1 Population Analysis Set

#### 8.2.1.1 GDX-44-015

Patients from the GDX-44-015 Per protocol population will be considered for the population PK analysis.

The Per Protocol Set (PPS) will include all patients in the Safety Set without major deviations likely to impact the population PK model.

Major deviation is defined as a deviation having an impact on the primary criteria. At minimum following protocol deviations will be stated as major in the trial:

- Patient not administered with gadopiclenol
- No plasma PK sample was obtained
- Concomitant treatment or procedure (e.g., diuretics, clinically significant blood loss or blood transfusion) that may alter gadopiclenol pharmacokinetic parameters
- All information regarding time of injection and times of PK sampling is missing.

- In the GDX-44-007 study, 3 PK profiles (children PPD ) and the first time point of 8 children ( PPD ) were considered as noteworthy outliers with unlikely PK profiles in the previous analysis and were not considered in the reference population analysis set. However, the final model was re-run with those children included in the analysis set as a sensitivity analysis.
- In the GDX-44-013 study, subject PPD was excluded due to major deviation from the clinical protocol.

No subject was excluded from the GDX-44-005 study.

### 8.3 ANALYSIS DATASETS

The analysis dataset will be created and formatted according to NONMEM requirement using SAS®.

The sponsor will provide values of gadopiclenol plasma concentrations measured, time of sampling, dose amount and information about compliance (date and time of dosing).

Moreover, subjects' demographic characteristics and any other data that could contain information valuable for the popPK model (covariates for example) will be provided to PhinC Development.

All data used for the NONMEM analysis dataset will be taken from the SDTM database. Data conversion to NONMEM structure will be performed using SAS® programming.

NONMEM dataset will be assembled using the actual date and time of all recorded administration and of samples of gadopiclenol.

A quality control (QC) will be performed between the source data and the final analysis dataset. Once controlled, the SAS® analysis dataset will be converted into an ASCII file readable by NONMEM and further used for PopPK analysis.

The inclusion of Japanese healthy volunteer data from GDX-44-013 study in this model will be performed later when the study on Japanese pediatric patients data will be completed and their data available for updating the model.

#### 8.3.1 Concentrations

All plasma concentrations of gadopiclenol with their actual date and time of sampling will be used for the popPK model.

Theoretical relative sampling times will be included in the dataset for reporting purpose only.

No concentration will be excluded a priori from the analysis unless the sampling date and/or time is missing and cannot be reasonably imputed by its theoretical value or when no dosing information (amount and time) before the sampling is available.

Exception will be made for excluded PK profiles from GDX-44-007 study (described in Section 8.2.1.2) which were considered as noteworthy outliers with unrealistic PK profile likely to bias the parameters estimation. They will be excluded from the analysis, consistently with previous analyses.

	PH21036 / GDX-44-015 Analysis Plan Version 2.0: 29/10/2024	gadopiclenol Page 13/30
---	---	----------------------------

### 8.3.2 Dosing events and design variables

Dosing information will be included in the database using the actual date and time of administration as well as the actual amount of drug administered. Dosing events will be entered in NONMEM dataset using the appropriate flag variables (EVID=1 and MDV=1).

### 8.3.3 Covariates

Continuous and categorical covariates may be used through the modelling to investigate their effect on PK parameters.

Categorical covariates will be handled as indicator variable for presence (covariate=1) or absence (covariate=0) for the factor.

Covariates (see section 9.5) will be fully defined in the data definition file, specifically the coding used for categorical covariates.

### 8.3.4 Missing data

#### 8.3.4.1 Dependent variable

Some distinction will be made between concentrations non-available due to values below the limit of quantification (BLQ) and missing data for any other reason (missing sample, not analyzed sample, premature discontinuation, etc.).

The number of BLQ data will be examined before the analysis. If BLQ samples represents no more than 15% of the total samples and does not appear to be dependent to a structural covariate, then BLQ values will be removed from the analysis dataset (M1 method as documented by Beal ). If BLQ samples represent more than 15% of the total samples or appeared to be dependent to a structural covariate, an alternative method will be considered (M3 or M4 described by Beal).

Missing PK concentrations data, for any other reason will not be replaced and will be set to missing in the analysis dataset using the missing dependent variable (MDV=1).

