#### **11.3.6 Population PK analysis**

The population PK analysis will be performed on the PPS using a dedicated software modelling and including pharmacokinetic models library.

The structural model describing the gadopiclenol concentrations profile as a function of time and amount of product injected will be first determined. Structural PK model parameters will enter the model either as fixed or random effects (when supporting a between-patient variability).

Covariates potentially influencing the PK of gadopiclenol will be tested using a backward sequential approach in order to prevent inflation of the type I error over the number of statistical tests.

Quality of the model will be assessed using goodness of fit plots and an internal validation will be performed using visual predictive checks.

Gadopiclenol plasma concentrations below the limit of quantification will be considered as missing, unless their proportion represent more than 15% of the total concentrations. In that case, alternative methods, such as left-censoring, will be considered for their contribution to the likelihood.

Empirical Bayes estimates (EBEs) of PK parameters (basically clearance and volume of distribution) will be obtained from the final model and summarized per age group and overall. In addition, the following parameters will be derived from the EBES, depending on the structural model retained for gadopiclenol:

 CONFIDENTIAL	Protocol No. GDX-44-015 Version No. 4.0 including amendments 1 & 2 & 3 Date 09 Oct 2023	F015919-05 Page 62 / 75
---	---	----------------------------

- Area Under the Curve,
- Elimination half-life,
- Total clearance,
- Volume of distribution.

In addition, gadopiclenol plasma concentrations at 10, 20 and 30 minutes post-injection will be simulated from the final model and their distribution will be summarized using box-plots and descriptive statistics by cohort, age group and overall.

All methods to be applied for the population modelling will be fully detailed in a dedicated analysis plan.

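### The 15% limit for deleting BLQ samples is counted over all samples, so it can tolerate heavy loss in the 6-8 h window that informs terminal half-life

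*SAP*

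**What the plan says.** SAP 8.3.4.1 sets two conditions for deletion. The first reads "If BLQ samples represents no more than 15% of the total samples"; the second, which must hold as well, is that BLQ status does not appear to depend on a structural covariate. When both hold, "then BLQ values will be removed from the analysis dataset (M1 method as documented by Beal" applies. The alternative branch opens "If BLQ samples represent more than 15% of the total samples or appeared to be dependent to a structural covariate"; in that case M3 or M4 is to be considered, not committed to.

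Protocol 11.3.6 has only the first condition: "Gadopiclenol plasma concentrations below the limit of quantification will be considered as missing, unless their proportion represent more than 15% of the total concentrations". Above that share, left-censoring is offered as something to consider.

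Three other parts of the plan bear on this:

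- Each patient gives three samples, one per window, and the only late one is W3 at 6-8 h (SAP 7.5).
- Elimination half-life is a primary criterion (Protocol 7.1) and is derived from the model's terminal slope (SAP 11).
- The analysis dataset is either the infants alone or the infants added to earlier studies, depending on the preliminary checks (SAP 9.1). The SAP does not say which total the 15% refers to in the pooled case.

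**The concern.** A limit on the overall BLQ share protects the fit only if BLQ values are spread over the sampling times. Here they should fall almost entirely in one window, which supplies a third of the samples and most of the information on the terminal phase. A share that looks small overall can therefore be a large share of W3.

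M1 keeps the higher late concentrations and discards the lower ones. That flattens the fitted terminal slope and lengthens the estimated half-life. The covariate condition does not address this directly. The structural covariates that SAP 9.5 lists are body weight, serum creatinine and ethnic group; sampling time is not among them.

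**Working it through.** **The plan's own figure.** The SAP plans 50 patients, "assuming that at least 45 patients will be evaluable for the PK" and "Assuming that about 10% of patients included in the trial will not be evaluable for the primary criteria". 45 / (1 - 0.10) = 50, which agrees.

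**Infants-only dataset.** Samples = 45 x 3 = 135. Limit = 0.15 x 135 = 20.25, so 20 BLQ values are allowed. If all fall in W3, 20/45 = 44.4%. With all 50 patients, 0.15 x 150 = 22.5, so 22 are allowed, and 22/50 = 44.0%. The ceiling falls if some BLQ values lie in W2: to 18/45 = 40% with two there, and to 15/45 = 33% with five.

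**Pooled dataset.** All 45 infant W3 samples stay within the limit when 45 <= 0.15 x (135 + P), that is, when the earlier studies contribute P >= 165 quantifiable samples. From Protocol 1.2, the dosed subjects in the three studies behind the current model are 36 + 12 (GDX-44-003), 40 (GDX-44-005) and 80 (GDX-44-007), or 168 in all. At only three samples each (a deliberately low assumption), the total is 504 + 135 = 639. The limit is then 0.15 x 639 = 95.85, so 95 are allowed, and 45/639 = 7.0%. The few exclusions in SAP 8.2.1.2 do not change this.

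**Would BLQ values fall in W3?** Inputs are the typical values in SAP Table 2 (CL 5.61, Q 4.15, V1 7.55, V2 4.80 at 70 kg), the SAP's allometric exponents, 0.05 mmol/kg, and the creatinine term set to 1. For an assumed 10 kg infant without maturation:

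- CL = 5.61 x (10/70)^0.75 = 1.30 L/h and Q = 0.964 L/h; V1 = 1.079 L and V2 = 0.686 L.
- k10 = 1.21, k12 = 0.894 and k21 = 1.41 per hour. The SAP 11 formula gives beta = 0.581 per hour and a half-life of 1.19 h.
- W3 is therefore about 5 to 7 half-lives after dosing. Predicted levels are 28.6 umol/L at 3 h and 2.8 umol/L at 7 h.

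Across assumed weights of 3.5 to 12 kg, with and without the renal maturation function of SAP 12.1, predictions are about 17-88 umol/L at 3 h and 0.8-23 umol/L at 7 h.

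**Size of the bias.** Two simulations of an infants-only fit were run, each with 45 infants, one sample per window, and maximum likelihood by Gauss-Hermite quadrature. Ages and weights were assumed.

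1. Protocol Table 3 values with SAP maturation, 30 trials per scenario, half-life at 12 months. The W3 share below is overall share x 135 / 45, taking all BLQ values to lie in W3.

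| Overall BLQ | Share of W3 | LLOQ set (ug/mL) | M1 median bias |
|---|---|---|---|
| 5% | 15% | 1.5 | +5% |
| 10% | 30% | 2.8 | +5% |
| 14.5% | 43% | 4.3 | +10% |

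M3 was within about 1% in all three, and CL was unaffected. With 30 trials per scenario and no Monte Carlo error available, the steps between rows should not be over-read.

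2. SAP Table 2 fixed effects, 70 trials per scenario, with the lowest 20 of 45 W3 values made BLQ.

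| Maturation | Variances from | M1 | M3 | All data |
|---|---|---|---|---|
| No | Protocol Table 3 | +4.7% | -0.9% | -1.1% |
| No | SAP Table 2 | +1.7% | -0.8% | -0.4% |
| Yes | Protocol Table 3 | +8.5% | -0.3% | -0.1% |
| Yes | SAP Table 2 | +5.9% | -0.5% | -0.5% |

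Entries are median errors in typical terminal half-life. Compared trial by trial with the uncensored fit, M1 was higher in 76-94% of trials. Median error in CL stayed within 1.2%.

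**The case against.** The strongest reply is that the SAP rule has two conditions. If late concentrations differ by body size, BLQ status depends on weight, a structural covariate, and the rule can leave M1 below 15%. In the second simulation BLQ status was indeed related to weight: the area under the ROC curve was 0.28-0.29 without maturation and 0.80-0.82 with it, against 0.5 for no relation. SAP 9.1 also treats population specificities as structural covariates, so an excess of BLQ values in infants within a pooled dataset could count as dependence. This stands, and it makes 44% an arithmetic ceiling, not a forecast. It does not close the gap. No test or cut-off is given, the outcome is only that another method is considered, and the protocol lacks the condition.

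The second reply is that the scenario may never arise. The documents name an LC-MS/MS assay but give no LLOQ. Reaching the ceiling needs an LLOQ near the median W3 level: about 1.7 umol/L without maturation, or 6.7 umol/L with it (6.7 x 0.970 = 6.5 ug/mL). Nothing in the documents suggests so insensitive an assay. This stands too.

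Third, the effect is modest. CL and AUC hardly move, no bias was shown for the 10, 20 and 30 minute concentrations, and the trial is descriptive. A shift of 2-10% lies inside 0.80-1.25, the range that SAP 9.6 uses for covariate effects, if that is borrowed as a yardstick. The plan also examines BLQ counts before analysis, tabulates them by window (SAP 13.1), and includes residual-versus-time plots and prediction-corrected checks. These could reveal late misfit, but no action is tied to them.

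A reader might go further and infer that the plan will lose 44% of W3, that half-life will be biased upward, or that the comparison between age groups will be distorted. The documents do not support this. The BLQ share is unknown. Bias by age group and in a pooled fit was not computed, and which infants have the lowest late levels depends on the maturation assumed.

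**Conclusion.** The concern holds in conditional form. The 15% limit uses a denominator that does not match where BLQ values should occur. It tolerates up to 20 of 45 W3 samples in an infants-only dataset, and all 45 if the pooled total is meant and the earlier studies supply at least 165 quantifiable samples. The covariate condition is a partial safeguard of uncertain effect.

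If the BLQ share approached the ceiling in an infants-only fit, typical terminal half-life would be overestimated by roughly 2-10% under M1, against about 1% or less under M3. CL and AUC would be almost unaffected. These sizes rest on assumed ages, weights and LLOQ, and on 30 to 70 simulated trials per scenario. If BLQ values prove rare, the choice makes no practical difference. The point matters because half-life is a primary criterion and the rule can be tightened now with a method the SAP already names.

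**What to change.** In SAP 8.3.4.1:

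- Count BLQ values on GDX-44-015 samples only, separately for each sampling window, whichever dataset is modelled.
- If any window exceeds the limit, use M3 (with the Laplacian option) as the main analysis and M1 as the sensitivity analysis.
- Below the limit, keep M1 as the main analysis but run M3 as a sensitivity analysis for half-life whenever there are BLQ samples. The 5% scenario above, which equals 15% of W3, still showed about +5% under M1. Making M3 the main method for a single BLQ sample would go further than the evidence requires.
- Commit to the alternative method when a trigger is met instead of only considering it. State the LLOQ and how covariate dependence will be judged.

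Align Protocol 11.3.6 with the revised SAP rule. The cost is a wording change, somewhat longer run times and possibly some convergence effort with M3.
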